### **Adipose tissue biopsies**

Participants will undergo a subcutaneous adipose tissue biopsy procedure during Joslin Visit 2 and Visit 6. For this procedure, participants will be properly positioned on an examination table. Prior to the biopsy a resting ECG (only during Visit 2, not Visit 6) will be obtained to ensure that there are no rhythm abnormalities or ST-T segment changes. The peri-umbilical area will be disinfected with betadine. Subsequently, the area will be anesthetized with a 1% lidocaine injection without epinephrine. As needed, EMLA crème may be applied prior to the start of the procedure, but this will be cleaned at the time of disinfection. Up to 5-10ml of 1% lidocaine may be used to ensure proper analgesia. After the peri-umbilical area has been disinfected and anesthetized, subsequently, a subcutaneous adipose tissue biopsy will be obtained with the Coleman Aspiration Cannula and Infiltration system and the Miller Medical 60cc Monoject Toomey and B-D Luer lock syringe. The needle will slowly be inserted into the subcutaneous adipose tissue at a 45 degree angle. If needed, an incision of a few millimeters may be made with a #11 blade. The needle will then be inserted and kept at a <45 degree angle. Up to 10ml of normal saline at any time can be infused subcutaneously, to facilitate dislodging of the adipose tissue. Negative pressure will be applied and the needle will be moved up and down the subcutaneous adipose tissue, while avoiding other tissues and the saline will be aspirated. When an adequate sample has been obtained, the area will be cleaned, a sterile gauze and a band-aid will be applied and manual pressure will be applied for up to 5 minutes. If there is inadequate sampling, the contralateral side may be used for a similar procedure. Aftercare instructions will be provided.

After the sample has been removed, blood clots will be removed from the sample. The largest piece of the adipose tissue will be prepared for histological analysis by formalin fixation. This will then be sent to the histology core at Beth Israel Deaconess Medical Center (BIDMC) for analysis. Samples will be prepared for H&E staining and up to 10 slides per sample will be prepared for immunohistochemistry. Immunohistochemistry will be performed to evaluate for markers of white adipose tissue browning. The remainder of the obtained adipose tissue will be processed by collagenase digestion and will then be quickly frozen in liquid nitrogen. The sample will then be prepared for mRNA and protein analysis.

Gene expression changes: In order better understand the effects of exercise training on subjects, we propose future investigation of changes in individual genes at the mRNA level by using microarray technology. The Joslin Diabetes Center's Genetics Core has been successful in performing these analyses on human subcutaneous adipose tissue. We would ask subjects consent to store the remainder of the subcutaneous adipose tissue and blood for further genetics testing, once consent has been obtained. Subjects may also opt out for this part of the study. No extra procedure will be involved.

### ***3. INCLUSION / EXCLUSION CRITERIA***

Approved by  
JDC/CHS 

**Inclusion Criteria:** For the MIT study, there will be three groups of subjects: 1) 28 lean subjects; 2) 28 overweight or obese subjects without type 2 diabetes; and 3) 10 overweight or obese subjects with type 2 diabetes. For the HIT study, there will be 10 lean subjects. Subjects will include equal numbers of males and females, aged 25-55 years, who have been cleared for regular exercise. All subjects will be sedentary according to American College of Sports Medicine's guidelines (6). Enrollment HbA1c values will be  $\leq 5.7 \pm 0.1\%$  for lean and overweight/obese subjects and between  $6.5\% \pm 0.1$ - $9.0 \pm 0.1\%$  for subjects with type 2 diabetes. BMI will be  $\geq 20 \pm 0.1$  and  $< 27 \text{ kg/m}^2$  for lean subjects,  $\geq 27$  and  $\leq 37 \pm 0.1 \text{ kg/m}^2$  for obese/overweight subjects, and  $\geq 25 \pm 0.1$  and  $\leq 37 \pm 0.1 \text{ kg/m}^2$  for subjects with type 2 diabetes. The study physician will review the participants' medical records for medical and treatment history to ensure the presence of type 2 diabetes. Subjects may be enrolled in the type 2 diabetes group if they meet diagnostic criteria during the screening visit (HbA1c, fasting plasma glucose or 2-hour OGTT). Participants must be following a sedentary lifestyle defined as less than 30 minutes of moderate to intense activity 3 days per week in the last 3 months at time of study enrollment (11). Participants must be cleared for exercise, including a  $\text{VO}_2$  peak test, by their clinician or the study physician. Lean subjects who enroll in the study will be randomized to either MIT or HIT training.

**Exclusion Criteria:** Potential participants will be excluded for the following criteria: Ages  $< 25$  and  $> 55$ ; HbA1c  $\leq 6.5 \pm 0.1\%$  and  $\geq 9 \pm 0.1\%$  for participants with type 2 diabetes (to maximize safety) and  $> 5.7 \pm 0.1\%$  for overweight or obese participants without diabetes; current smoking status, type 1 diabetes, heart or lung disease; acute systemic infection accompanied by fever, body aches, or swollen lymph glands; current dieting or weight loss efforts; current pregnancy; known history of HIV/AIDS; cancer; biochemical evidence of renal or hepatic dysfunction; End-Stage Renal Disease and any renal disease, defined as a creatinine above the normal limit; liver disease; demyelinating diseases such as multiple sclerosis or amyotrophic lateral sclerosis; recent blood donation; clinical history of stroke; severe hypertension (systolic  $> 160 \text{ mmHg}$  or diastolic  $> 90 \text{ mmHg}$ ); type 1 diabetes; history of keloid formation, and inability to exercise at 50% of predicted heart rate (HR) reserve at baseline. Participants taking beta-blockers, thiazolidinedione, and a basal-bolus insulin regimen will be excluded as well. Participants will also be excluded if during Joslin Visit 1, participants without established type 2 diabetes reach a glucose value of 140mg/dl or higher at the 2 hour point during the oral glucose tolerance test.

Either a current pregnancy or breastfeeding are exclusion criteria for this study, in particular for scientific reasons, since pregnancy and breastfeeding may affect myokine and adipokine secretion and interfere with the ability to exercise. To confirm that a female subject is not pregnant prior to participating in the study, a urine pregnancy test will be performed at Joslin Visit 1. Pregnancy tests will be repeated prior to performing any DXA body composition analysis for female participants if greater than 10 days have passed since prior testing. If a positive result is found, this assessment will not be performed. Participants will also be asked to use contraception during the remainder of the study.

Participants who screen positive for The American Heart Association's contraindications to exercise testing (10) (see Appendix) during pre-enrollment screening by the study physician or their clinician are ineligible for this study.

Potential participants will also be excluded if they have severe complications from diabetes, including the following: severe peripheral diabetic neuropathy and/or severe peripheral vascular disease, symptomatic severe autonomic neuropathy, nephropathy (microalbumin/creatinine ratio  $> 300 \text{ mg/g}$ ), and untreated proliferative diabetic retinopathy based on dilated eye examination within one year of study entry.

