### Subject Visits.

Pre-training visits 1, 2 and 3 will be scheduled within four weeks of each other and the order of visits may be reversed. Visit 4 will occur halfway through the exercise training program. Visit 5 will be done in lieu of the first or second training session of week 10. Visit 6 will be within 24 hours of the last training session, and Visit 7 will occur up to 3 days before or after visit 6. Visits 2 and 3, and 5, 6 and 7 may be scheduled in different order, if absolutely necessary to accommodate subject's schedules.

Testing Visit 1. Subjects will arrive between 8 and 9AM after an overnight fast of at least 8 hours. During the pre-screening, subjects will be informed about this requirement and medication instructions will be given. This information will also be mailed or emailed to the subject. At the first visit, before initiating any procedures, the study will first be explained to the participant in detail and consent forms will be signed (see below). Subjects will be asked in anticipation of this visit to hold their medication the morning of the visit (this is the same for any visit requiring fasting). The participant's medical history, blood pressure, height, weight, and BMI (weight in kilograms divided by height in meters squared) will be obtained. An estimate of body composition will be obtained by performing a DXA body composition analysis (only for lean and overweight/obese subjects in the MIT training group). Briefly, the Hologic DXA system will be used, which provides images for assessment of bone density, and body fat composition. Images will be obtained by an experienced technician. Pregnant women are excluded from the study. Participants must not have had any radiographic barium studies within the past week, as this will be seen in the digestive track and interfere with the measurement of bone densitometry. Any metallic implants or previous fractures are not a contraindication for the scan, but will be annotated

Approved by  
JDC/CHS

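### Repeat pregnancy tests follow only the DXA scan, so about 10 of 38 planned women have none after Visit 1, and no rule covers a positive test once training has begun

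*Combined protocol and SAP*

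**What the plan says.** Section 3 (Exclusion Criteria) states: "Either a current pregnancy or breastfeeding are exclusion criteria for this study". The reason given is scientific: "since pregnancy and breastfeeding may affect myokine and adipokine secretion and interfere with the ability to exercise". All women are tested at Visit 1. After that, "Pregnancy tests will be repeated prior to performing any DXA body composition analysis for female participants if greater than 10 days have passed", and the stated result is: "If a positive result is found, this assessment will not be performed". Section 3 adds: "Participants will also be asked to use contraception during the remainder of the study".

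Section 2 repeats the link to the scan. Under Testing Visit 1, a baseline DXA done more than 10 days after the first test needs a new one. Under Testing Visit 7, a test precedes the final DXA, here without a 10-day condition. In both places a positive result cancels the scan.

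The scan is "only for lean and overweight/obese subjects in the MIT training group". The same description of the scan also says, without condition, that pregnancy excludes a woman from the study. On timing, "Pre-training visits 1, 2 and 3 will be scheduled within four weeks of each other". Visit 2 is the biopsy, and Visit 3 is the VO2peak test and training day 1.

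**The concern.** The reasons given for excluding pregnancy concern adipokines and exercise capacity, yet retesting follows only the X-ray. Before a scan, a test counts as out of date after 10 days. Before a maximal exercise test, a biopsy or ten weeks of training there is no such limit.

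Two things are at stake. The first is participant safety: a woman who conceives after Visit 1 could start training, or go through to the second VO2peak test and biopsy, without anyone looking for a pregnancy. The second is the data. VO2peak and novel adipokines are primary outcomes in Section 4, and they are what Section 3 says pregnancy may disturb. Groups are small: one woman is 1 of 10 in the type 2 diabetes or high-intensity (HIT) group and 1 of 14 in a sex-specific MIT cell.

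**Working it through.** The plan gives no figure on this point to reproduce. The check is an inventory of tests, a head count and a timeline.

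**Inventory**

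| Place | When a test is required | Stated consequence of a positive result |
|---|---|---|
| Section 3, Visit 1 test | All women | Pregnancy is an exclusion |
| Section 3, repeat test | Before a DXA, if the last test is over 10 days old | Scan not done |
| Section 2, Testing Visit 1 | Before a baseline DXA, if over 10 days | Scan not done |
| Section 2, Testing Visit 7 | Before the final DXA | Scan not done |
| Visits 2 and 6 (biopsy), 3 and 5 (VO2peak), 3b, 4, and both training programs | None | None |

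**Head count** (group sizes from Sections 2 and 3; "Subjects will include equal numbers of males and females")

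- Participants: 28 + 28 + 10 + 10 = 76. Women: 76 / 2 = 38.
- Women with a DXA: 14 + 14 = 28, and 28 / 38 = 74%.
- Women without a DXA: 38 − 28 = 10 (5 type 2 diabetes, 5 HIT), and 10 / 38 = 26%.

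**Timeline**

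- The 10 women without a DXA rely on one test for up to 4 + 10 = 14 weeks, if the full four-week baseline window is used.
- Scheduled retests before training: 0 of 38 if each DXA is done at Visit 1, and at most 28 of 38 if every scan is deferred to Visit 2 or 3 and falls more than 10 days after the first test. Even then the test has to precede the scan; nothing requires it to precede that day's biopsy or exercise test.
- At the end, Visit 5 (second VO2peak) is in week 10, Visit 6 (second biopsy) is within 24 hours of the last session, and Visit 7 is up to 3 days either side of Visit 6. The final retest can therefore fall after both procedures. The scan may be moved to Visit 5 or 6, but this is a scheduling option.

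**Consequence of a positive result**

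- Before training: the exclusion in Section 3 and the sentence in the Visit 1 DXA description both apply, so the woman is already ineligible.
- After training has begun: the repeat-test wording only cancels the scan. Section 4 lets the study physician advise stopping on medical grounds, and Section 11 mentions unforeseen findings that end eligibility. Neither names pregnancy or refers to a test result.

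**What added tests would leave**

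- With tests at baseline and before the first of Visits 5 and 6, the untested stretch runs from week 1 to week 10: 10 − 1 = about 9 weeks.
- With one more at Visit 4 (week 5), the stretches are 5 − 1 = about 4 and 10 − 5 = about 5 weeks.
- Under a 10-day rule, the baseline test may itself be up to 10 days old at Visit 3.

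**The case against.** The other side has a good case. Linking the retest to the one procedure that uses ionising radiation, after a test for all women at Visit 1 and with contraception requested, is a coherent choice in proportion to risk. The plan says that pregnant women are excluded, and cancelling the scan may be only the same-day instruction. Section 6 requires a history, examination and ECG before the VO2peak test, and subjects with type 2 diabetes see the study physician at weeks 3, 6 and 10. No passage says that the biopsy, the exercise test or training harms a pregnancy.

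Much of this stands. A reader might infer that a woman testing positive before training would simply miss her scan and carry on; the exclusion wording does not support that. A reader might also infer that the plan knowingly exposes women to harm, or that the male-female comparison is biased. The documents show neither, and the size of any such effect cannot be derived.

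What does not stand is that these provisions do the work of a test. None schedules one, the physician visits cover only the diabetes regimen in one group, and an exclusion cannot act on a pregnancy that nobody has looked for.

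**Conclusion.** The point holds as a cheap improvement to participant safety and to the primary outcomes; it is not a flaw that threatens the trial. About 10 of 38 planned women have no scheduled test after Visit 1. The other 28 have none before training if the scan is done at Visit 1, and their last test can come after the final VO2peak test and biopsy. No available text says what follows a positive test once training has begun.

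The counts assume the planned group sizes and an equal sex split. They are upper bounds on women at risk, since ages run to 55 and some will be unable to conceive. The 14 weeks assume the longest baseline window. The number who would become pregnant cannot be derived and is probably small, given the contraception request. The consent pages, a short part after the data-monitoring text and the appendix of contraindications were not in the text available, so a rule there cannot be ruled out.

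A reader might also infer that a with-and-without analysis of affected women is needed. It would have almost nothing to compare: a woman stopped before Visits 5 and 6 has no post-training VO2peak or adipose sample.

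**What to change.** 1. In all four groups, repeat the urine test before the baseline biopsy (Visit 2) and before the baseline VO2peak test and start of training (Visit 3), each time only if the last test is more than 10 days old. Repeat it for all women before the first of Visits 5 and 6.
2. State that a positive test during the study stops VO2peak tests, biopsies and DXA, and refers the woman to the study physician about continuing exercise. For a positive test before training, point to the existing exclusion.
3. Consider a further test at Visit 4. Without it, about nine weeks of training stay untested; with it, the longest stretch is about five.

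Cost of items 1 and 2: a short amendment and one to three urine tests per woman. That is 38 × 1 = 38 tests if Visits 2 and 3 both fall within 10 days of the Visit 1 test, and 38 × 3 = 114 at most. Item 3 adds 38, giving 76 to 152. The Visit 7 wording has no 10-day condition, so a separate test before the final DXA may still be needed in the 28 women scanned. There may be a few more screen failures.

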#### **4. DATA ANALYSIS / SUBJECT SELECTION**

##### **Sample Size**

Approved by  
JDC/CHS 

The initial sample size calculation of this study was done in consultation with [REDACTED] through Harvard Catalyst's biostatistical consulting service. The initial study design consisted of four study groups with a sample size of  $N = 10$  in each of the four groups. These analyses will provide an estimate of effect size. The data collected in our study are unique and sample size estimates cannot be based on previous human studies as ours is the first study to investigate how short-term exercise training impacts these novel adipokines in obesity and type 2 diabetes and few studies have evaluated scWAT beiging. However, sample size calculation in collaboration with the Harvard Catalyst biostatistician team revealed that a sample size of 9 in each group will have power of 0.85 to detect a change of 2.8 ml/kg/min in  $\text{VO}_{2\text{peak}}$ , assuming a standard deviation of that change of 2.4 based on a linear mixed models (repeated measures) analysis framework at an alpha of 0.05. Since we are interested in the effects of exercise training on changes in human adipose tissue as a primary outcome, we also calculated the sample size needed to detect changes in TGF-beta 2 mRNA expression. A sample size of 8 in each group will have similar power to detect a difference in fold change of between 1.53-1.91 (SD 0.5) over basal in adipose tissue TGF-beta 2 mRNA expression levels. The fold increase in mouse serum TGF-beta 2 after exercise was 1.56 (SD 0.5), in line with and supporting our sample size calculations based on mRNA expression. Analysis of preliminary data examining the change in UCP1 mRNA levels suggests similar magnitude of effect (i.e. fold-change on the order of 2.0 with exercise training) with a more variable response (SD of change equal to size of change), and consequently 12 subjects would be required to achieve a power of 0.88 to detect this effect at an alpha of 0.05. Conversely, with the planned sample size of 10 per group, we estimate a power of 0.80 to detect this effect size at an alpha of 0.05 in the planned analyses. We anticipate that 90% of volunteers will comply with the study protocol and, therefore, plan to include a total of 11 participants in each group.

These original power calculations did not include an adequate number of subjects to discern differences between males and females. We have secured additional funding to determine sex-specific effects of moderate intensity exercise training on adipose tissue metabolism in lean and overweight subjects. Thus, we will increase the enrollment numbers for these two specific groups of subjects, to allow for adequate power to identify sex-specific changes in adipose tissue metabolism. The expanded groups will include: 14 lean males, 14 lean females, 14 overweight/obese males, 14 overweight/obese females, all undergoing moderate intensity exercise training.

We will evaluate changes in adipose tissue and serum as defined in the Specific Aims. Univariate analysis will be used to examine potential outliers and missing data. Categorical variables will be summarized and presented using frequencies and proportions while continuous variables will be summarized and presented using means, medians and standard deviations.

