## 2. STUDY DESIGN:

### Subjects

In this section, we will provide the study design in terms of subject recruitment, exclusion criteria, visit details, exercise training program, and sample collection.

There will be two exercise training regimens. The first training regimen will determine the effects of moderate intensity endurance exercise training on scWAT in lean, healthy overweight/obese, and overweight/obese subjects with type 2 diabetes (MIT study group). The second training regimen will determine the effects of high-intensity interval training (HIT) in lean subjects (HIT study group). For both studies, the visit details, acute exercise experiments, and sample collection will be similar so they are described together.

**Subjects.** For the MIT study, there will be three groups of subjects: 1) 28 lean subjects; 2) 28 overweight or obese subjects without type 2 diabetes; and 3) 10 overweight or obese subjects with type 2 diabetes. For the HIT study, there will be 10 lean subjects. Subjects will include equal numbers of males and females, aged 25-55 years, who have been cleared for regular exercise. All subjects will be sedentary according to American College of Sports Medicine's guidelines (6). Enrollment HbA1c

[figure not shown]
Approved by  
JDC/CHS 

values will be  $\leq 5.7 \pm 0.1\%$  for lean and overweight/obese subjects and between  $6.5 \pm 0.1\%-9.0 \pm 0.1\%$  for subjects with type 2 diabetes. BMI will be between  $\geq 20 \pm 0.1$  and  $< 27 \text{ kg/m}^2$  for lean subjects,  $\geq 27$  and  $\leq 37 \pm 0.1 \text{ kg/m}^2$  for obese/overweight subjects, and  $\geq 25 \pm 0.1$  and  $\leq 37 \pm 0.1 \text{ kg/m}^2$  for subjects with type 2 diabetes.

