**HIT Exercise Training Program.** Ten lean subjects will be randomized to a high-intensity interval (HIT) training program, which will be outlined to the subjects. The total number of HI efforts each session will increase over the 10-week training period. For the initial two interval sessions, HIT training will consist of 4 x 30s all-out cycling efforts (HI) with 4min of recovery (LI; 15-25% PPO) between HI efforts. For the 3rd and 4th training sessions, 5 x 30s efforts will be performed. For the remainder of the sessions, the subject will perform 6 x 30s HI efforts. Each exercise bout will start with 5 sec of acceleration with light resistance to the maximal cadence followed by a sudden increase in resistance (starting at 100% of peak power output from VO2 assessment and adjusted as necessary) and continued with maximal effort cycling for 30s. The HIT Exercise Training Program will be performed at Joslin three times/week without an 'at home' component. If illness or travel prevents attending any of the required exercise sessions, the missed time will be made up at the latter half of the 10-week period.

For both the MIT and HIT exercise training program, subjects may perform the exercise training session at Joslin both during normal business hours (8am-5pm) and outside normal business hours in coordination with the exercise physiologist. Outside regular business hours, emergency medical assistance at Joslin may not be readily available and subjects may need to proceed to the ER in case medical assistance is needed.

**Activity Assessments:** To confirm that participants are sedentary pre-intervention, we will assess their physical activity by physical activity recall for the last three months during Joslin Visit 1. Participants will be considered sedentary according to the most current guidelines of the American College of Sports

Approved by  
JDC/CHS 

Medicine if they meet the following criteria: sedentary lifestyle is defined as not participating in at least 30 minutes of moderate intensity physical activity (estimated at 40-60% VO2 reserve) on at least three days of the week for at least 3 months (9). Self-reported data regarding their level of activity from the pre-screening will be used to determine eligibility.

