## **8. RECRUITMENT / SOURCE OF SUBJECTS:**

Current Joslin patients who meet study criteria may be contacted through letter, and flyers will also be placed around the Longwood Medical Area neighborhood and inside the Joslin Diabetes Center. To recruit non-Joslin patients and participants without diabetes, the use of online social media and job recruitment websites (i.e. Facebook, Craigslist, university job websites, etc.) will help identify potential participants. Additionally, we will be using the company Trialfacts to help recruit participants for the study, which uses recruitment websites including Facebook, Instagram and targeted ads on websites. The website for Boston University's online job application can be found here:

[http://www.bu.edu/link/bin/uiscqj\\_student\\_employment.pl/uismpl?ModuleName=se\\_job.pl](http://www.bu.edu/link/bin/uiscqj_student_employment.pl/uismpl?ModuleName=se_job.pl)

Approved by  
JDC/CHS 

Fliers with contact information that potential participants can contact regarding the study will also be placed at appropriate and approved buildings and academic institutions around the Longwood Medical Area. Examples of these buildings would include: Karp Research Building at Boston Children's Hospital, Simmons University, and the Longwood Galleria. If these methods do not identify enough potential participants, an ad will be placed in a local newspaper. Some eligible participants have already been identified by Joslin colleagues and these individuals will also be contacted.

We will enroll 38 lean participants, 28 overweight/obese participants and 10 participants with type 2 diabetes. Current studies with exercise components, including the Why Wait and LookAhead programs have 85% and 95% retention rates, respectively. Since the intervention is relatively short, the retention should be quite high. To further encourage retention, we will compensate participants for their time spent attending assessment appointments and exercising, and they will receive the exercise program free of charge. We will also provide participants with parking in the Harvard/Longwood Medical area.

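### The type 2 diabetes and HIT groups are set at 10, although the sample size section plans 11 per group to allow for 90% compliance

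*Combined protocol and SAP*

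**What the plan says.** The first paragraph of Sample Size (Section 4) treats UCP1 mRNA as a change whose SD equals its size, at alpha 0.05. It quotes power of 0.88 with 12 subjects and adds that "with the planned sample size of 10 per group, we estimate a power of 0.80 to detect this effect size". It then anticipates 90% compliance and concludes that the investigators "plan to include a total of 11 participants in each group".

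The sections that set intake give other numbers for two of the four groups:

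- Section 2, Subjects: "10 overweight or obese subjects with type 2 diabetes. For the HIT study, there will be 10 lean subjects".
- Section 2, HIT Exercise Training Program (HIT only): "Ten lean subjects will be randomized to a high-intensity interval (HIT) training program".
- Section 3, Inclusion Criteria: the same 10 for type 2 diabetes, and "For the HIT study, there will be 10 lean subjects".
- Section 8, Recruitment: "We will enroll 38 lean participants, 28 overweight/obese participants and 10 participants with type 2 diabetes". The 38 lean are 28 moderate-intensity plus 10 HIT, so HIT is 10 here by subtraction.

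The next paragraph of Sample Size describes the expansion made with additional funding: "we will increase the enrollment numbers for these two specific groups of subjects". The two groups are lean and overweight/obese, both on moderate-intensity training and now 28 each. The type 2 diabetes and HIT groups are not mentioned.

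**The concern.** Sample Size derives 11 from the compliance rate, so 11 is the intake and 10 is roughly the number meant to remain. The other sections use words of intake, enrolling and randomising, and attach them to 10. Read together, the two small groups have no allowance for non-compliance, while the stated 0.80 assumes that all 10 contribute.

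UCP1 is a beiging marker under Specific Aim 1, and type 2 diabetes is one of the populations that aim names. The 0.80 is the only UCP1 power given for the planned group size. A reader cannot tell whether 76 or 78 people will be enrolled, or whether the 0.80 already allows for non-compliance.

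**Working it through.** **Inputs from the plan.** From Sample Size: SD of the UCP1 change equal to the change, so the standardised effect is d = 1; alpha 0.05; 90% compliance. From Sections 2, 3 and 8: 10 enrolled in each of the type 2 diabetes and HIT groups. Sidedness and the exact test behind the power figures are not stated.

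**Step 1: reproduce the plan's figures.** For a paired t-test on n changes, the statistic is noncentral t with n − 1 degrees of freedom and noncentrality d√n. Two-sided power is P(|T| > t at 0.975 with n − 1 df).

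| Evaluable n | Noncentrality | Power | Plan states |
|---|---|---|---|
| 9 | 3.00 | 0.748 | – |
| 10 | 3.16 | 0.803 | 0.80 |
| 11 | 3.32 | 0.848 | – |
| 12 | 3.46 | 0.883 | 0.88 |

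Both stated values reproduce. At n = 10 the alternatives do not: one-sided paired t 0.898, normal approximation 0.885, two-sample t 0.562. On the same test the VO2peak figure (d = 2.8/2.4, n = 9) comes to 0.864 against a stated 0.85.

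**Step 2: apply the plan's compliance rate.** 10 × 0.90 = 9 evaluable, giving 0.748. With the planned 11, 11 × 0.90 = 9.9, giving about 0.80. Strictly, 10/0.90 = 11.1, which rounds up to 12, but 11 is close enough not to matter.

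**Step 3: let the number evaluable vary.** Power averaged over a binomial number of evaluable participants, with non-compliers not evaluable:

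| Enrolled | Proportion evaluable | Average power |
|---|---|---|
| 11 | 0.90 | 0.793 |
| 10 | 0.90 | 0.742 |
| 10 | 0.85 | 0.708 |
| 10 | 0.95 | 0.774 |

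The 85% and 95% rows use the retention rates cited in Section 8. With independent 90% completion, the chance of fewer than 10 evaluable is 1 − 0.9^10 = 0.65 when 10 are enrolled and 1 − 0.697 = 0.30 when 11 are enrolled.

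**Step 4: non-compliers kept in the analysis.** With 10 analysed, nine with a mean change of 1 SD and one with a reduced mean, paired-t power is 0.80 if the tenth responds fully. By simulation it is 0.754 with half the response and 0.684 with none.

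**Step 5: the planned model.** Analysis of Primary Outcomes specifies a four-group repeated measures ANOVA. If it pools error variance (equal variances, no multiplicity adjustment), the noncentrality stays d√n and the error degrees of freedom become the total evaluable minus 4.

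| Groups evaluable | df | n in small group | Power |
|---|---|---|---|
| 9, 9, 9, 9 | 32 | 9 | 0.829 |
| 9, 9, 25, 25 | 64 | 9 | 0.840 |
| 10, 10, 10, 10 | 36 | 10 | 0.868 |
| 10, 10, 28, 28 | 72 | 10 | 0.877 |

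Pooling does not reproduce the stated 0.80 at n = 10, so it is a sensitivity case. The cost of one participant is 0.803 − 0.748 = 0.055 for the paired test, and 0.868 − 0.829 = 0.039 or 0.877 − 0.840 = 0.037 under pooling.

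**Step 6: enrolment totals.** As written in Sections 2, 3 and 8: 28 + 28 + 10 + 10 = 76. With 11 in the two small groups: 28 + 28 + 11 + 11 = 78.

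**The case against.** The best defence is that the power loss, unlike the mismatch, depends on conditions the documents never state. No section removes non-compliers from analysis, and Testing Visits 2 and 6 allow a repeat biopsy, so all 10 could be evaluable and power would be 0.80 as claimed. The plan also ties the 0.80 to its planned analyses, which are a four-group model, and with pooled error 9 evaluable participants still exceed 0.80. Both points stand. They make the 0.75 conditional, but they do not restore the missing allowance.

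A second argument is that the 11 is left over from an earlier design: the paragraph opens as an initial calculation and the next one refers back to original calculations. That may explain how the mismatch arose. It does not resolve it, because the expansion revises only two groups and the first paragraph remains the sole sample-size basis for the other two.

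Third, the effect is minor beside the uncertainty in the inputs. The background section reports a 1.8-fold UCP1 increase where Sample Size assumes about 2.0. As an illustration only, a change of 0.8 with the SD held at 1.0 gives power of 0.62 at n = 10. The plan already asks for caution because of small samples. This is fair and limits the weight of the point, but a stated size and allowance that two groups do not receive should still be corrected.

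**Conclusion.** The concern holds. The plan states 11 per group with a compliance allowance, and its intake sections set the type 2 diabetes and HIT groups at 10 without one. That contradiction needs no power assumption.

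UCP1 power in those two groups is about 0.75 rather than 0.80, provided that non-compliers give no evaluable biopsy pair, 9 of 10 remain, and the test is the two-sided paired t that reproduces the plan's own 0.80 and 0.88. With pooled error variance, power stays above 0.80. The mismatch is worth fixing, but its effect is small. The stated sizes of 9 for VO2peak and 8 for TGF-beta 2 are met with 9 evaluable, and the two groups of 28 are not affected.

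**What to change.** Decide which number is meant and make Sample Size agree with Section 2 (Subjects and HIT Exercise Training Program), Section 3 and Section 8.

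**If enrolment stays at 10**, replace the last sentence of the first Sample Size paragraph with:

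> We anticipate 90% compliance. With 10 enrolled in the type 2 diabetes and HIT groups, about 9 evaluable participants are expected in each if non-compliers provide no evaluable biopsy pair, giving power of about 0.75 for the within-group pre/post change in UCP1 (change equal to its SD, paired t-test, two-sided alpha 0.05).

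Name the same test beside the 0.80 in the preceding sentence, which refers only to the planned analyses, so that the two figures are on one basis. This costs wording only, and a slightly less favourable stated power in two groups.

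**If 11 is meant**, change 10 to 11 for both groups in Subjects and in Section 3, ten to eleven in the HIT programme, and in Section 8 change 38 lean to 39 and 10 with type 2 diabetes to 11. This costs two more participants. It also conflicts with the statement that "Subjects will include equal numbers of males and females", since 11 cannot be split equally, so that sentence would need an exception.
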